### **Dose Modifications for Liver Toxicity**

Dose reductions of study treatment should be considered in any subject who develops drug-related Grade 2 elevated ALT, AST, or bilirubin lasting longer than 1 week. A subject who develops Grade  $\geq 3$  elevated ALT, AST, or bilirubin should have study treatment held and restarted at a reduced dose (see Appendix VI) after ALT, AST, and bilirubin levels resolve to at least Grade  $\leq 1$  or baseline. In subjects with recurrence of drug-related Grade  $\geq 3$  elevated ALT, AST, or bilirubin at the lowest dose level, study treatment should be discontinued. In subjects who develop ALT/AST elevations  $> 3 \times$  ULN in combination with a bilirubin elevation  $> 2 \times$  ULN without reasonable other explanation, drug-induced liver injury should be suspected and cabozantinib treatment interrupted.

### **Dose Modifications for Pancreatic Toxicity**

Cabozantinib should be held if patient experiences Grade 3 asymptomatic amylase or lipase elevation. Elevated laboratory parameters should be checked at least twice weekly until  $\leq$  Grade 1.

If lab values do not resolve to  $\leq 1$  Grade within 7 days of interruption or if toxicity recurs with re-challenge at reduced dose, then this will be considered dose-limiting. Cabozantinib will then be discontinued.

### **Dose Modifications for Diarrhea**

If dose-limiting Grade 3 ( $> 3$  days) or Grade 4 therapy-associated diarrhea is experienced by a patient despite maximal use of anti-diarrheal medications, the dose of cabozantinib should be reduced. Loperamide should be used at the first sign of significant diarrhea.

Subjects should be instructed to notify their physician immediately at the first signs of poorly formed or loose stool or an increased frequency of bowel movements. Administration of antidiarrheal/antimotility agents is recommended at the first sign of diarrhea as initial management. Some subjects may require concomitant treatment with more than one antidiarrheal agent. When therapy with antidiarrheal agents does not control the diarrhea to tolerable levels, study treatment should be temporarily interrupted or dose reduced per table at beginning of section 7.1.

In addition, general supportive measures should be implemented including hydration, correction of fluid and electrolyte abnormalities, small frequent meals, and stopping lactose-containing products, high fat meals, and alcohol.

## Dose Modifications for Palmar Plantar Erythrodyesthesia (PPE)

CTCAE v.5.0 Grade	Action To Be Taken
Grade 1	Study treatment may be continued at the current dose if PPES is clinically insignificant and tolerable. Otherwise, study treatment should be reduced to the next lower dose level. a Start urea 20% cream twice daily AND clobetasol 0.05% cream once daily. Reassess at least weekly; if PPES worsens at any time or does not improve after 2 weeks, proceed to the intervention guidelines for Grade 2.
Grade 2	Study treatment may be continued if PPES is tolerated. Study treatment should be dose reduced or interrupted if PPES is intolerable. Continue urea 20% cream twice daily AND clobetasol 0.05% cream once daily and add analgesics (eg, NSAIDs/gamma-aminobutyric acid agonists) for pain control if needed. Reassess at least weekly; if PPES worsens or affects self-care, proceed to the intervention guidelines for Grade 3.
Grade 3	Interrupt study treatment until severity decreases to Grade 1 or 0. Continue treatment of skin reaction with clobetasol 0.05% cream twice daily AND analgesics. Resume study drug at a reduced dose if PPES recovers to Grade $\leq$ 1. Discontinue subject from study treatment if PPES does not improve within 6 weeks.

CTCAE, Common Terminology Criteria for Adverse Events; NSAID, non-steroidal anti-inflammatory drug; PPES, palmar plantar erythrodyesthesia syndrome.

a Permitted dose levels are defined by individual protocols.

## 7.2 Supportive Care and Other Concomitant Therapy

### Concurrent Anticancer Therapy

Concurrent cancer therapy, including chemotherapy, radiation therapy, immunotherapy, or biologic therapy may NOT be administered to subjects receiving study drug. If these treatments are administered the subject will be removed from protocol therapy.

### Investigational Agents

No other investigational agents may be given while the subject is on study.

### Supportive Care

Appropriate antibiotics, blood products, anti-emetics, fluids, electrolytes and general supportive care are to be used as necessary. See Appendix III and V for drugs that should not be used concomitantly due to potential interactions with cabozantinib.

Diarrhea is a common side effect of cabozantinib. Loperamide should be used at the first sign of significant diarrhea.

Palmar-plantar erythrodysesthesia syndrome (PPE; also known as hand-foot syndrome) is a common side effect of cabozantinib. Careful attention should be paid to skin exams and supportive care instituted early if any swelling or erythematous skin changes or symptoms of pain or burning/tingling are noted. Subjects should be instructed to apply moisturizing creams, avoid any trauma, harsh chemicals and limit hot water exposure. Topical steroid creams may be used and consider early dermatology referral.

### **Growth Factors**

Growth factors that support platelet or white cell number or function can only be administered for culture proven bacteremia or invasive fungal infection. The Study Chair should be notified before growth factors are initiated.

### **Concomitant Medications**

Medications that are strong inhibitors or inducers of CYP3A4 should be avoided

The use of enzyme inducing anticonvulsants is not permitted.

Medications that prolong the QT interval and have a known or possible risk of Torsades de Pointes should be avoided if possible, but are not explicitly excluded see appendix IV. If the subject starts a medication with substantial evidence that the drug prolongs the QT interval, then ECG monitoring must be end of each cycle while on the medication

### **Wound Healing and Surgery**

VEGFR inhibitors can cause wound healing complications and wound dehiscence which may occur even long after a wound has been considered healed. Therefore, surgical and traumatic wounds must have completely healed before starting cabozantinib treatment and be monitored for wound dehiscence or wound infection while the subject is being treated with cabozantinib. Subjects should not have elective surgical procedures while on therapy. If possible, cabozantinib treatment should be stopped for at least 28 days prior to major surgery. For subjects who require emergent or urgent procedures, therapy may not be restarted until 28 days after major procedures and 7 days after minor procedures such as line replacement (3 days for external lines [e.g. Hickman or Broviac]).

### **Thromboembolic Events**

Thromboembolic complications are frequent in cancer patients due to procoagulant changes induced by the malignancy or anticancer therapy including inhibitors of VEGF pathways. Deep vein thrombosis and PE have been observed in clinical studies with cabozantinib; including fatal events (please refer to the Investigator's Brochure). The risk of hemorrhage in cabozantinib-treated subjects with brain metastases has not been thoroughly analyzed. The incidence of CNS hemorrhage events in a study of subjects with GBM was higher than observed in general population of subjects with cancer treated with cabozantinib. Based on this observation, any subjects on this study will be taken off study if DVT occurs and anticoagulation is required to reduce the risk of hemorrhage of subjects on study. Subjects who require anticoagulation for any reason will be considered off-study.

Subjects with DVT who may require anticoagulant therapy will be taken off study.

Arterial thrombotic events (eg, transient ischemic attack, myocardial infarction) have been observed in studies with cabozantinib. Subjects should be evaluated for preexisting risk factors for arterial thrombotic events such as diabetes mellitus, hyperlipidemia, hypertension, coronary artery disease, history of tobacco use, and cardiac or thromboembolic events that occurred before initiation of study treatment. Cabozantinib treatment should be discontinued in subjects who develop an acute myocardial infarction, cerebral infarction or any other clinically relevant arterial thromboembolic complication.

### **Concurrent Anti-Hypertensive Therapy**

The algorithm above (See Section 7.1) will be used to grade and manage cabozantinib related hypertension. Should initiation of anti-hypertensive therapy be required, single agent therapy (commonly including the calcium channel blockers amlodipine or nifedipine, which are permissible without discussion with the study chair) should be started and the blood pressure should be monitored at least twice weekly until BP is within the 95th percentile for age, height, and gender.

### **Management of Hypothyroidism**

Subjects with Grade 2 hypothyroidism adequately managed with thyroid hormone replacement may continue on protocol therapy. Subjects with Grade 3 or greater hypothyroidism will be considered to have had a dose-limiting toxicity. These subjects should be managed according to guidelines for non-hematologic toxicity and should also be evaluated by an endocrinologist for further management. Subjects who enter the study on thyroid replacement should have their medication adjusted to maintain TSH in the normal range.

### Corrected QT Prolongation

If at any time on study there is an increase in QTcF to an absolute value > 500 ms or an increase of > 60 ms above baseline, two additional ECGs must be performed with intervals not less than 3 min apart within 30 min after the initial ECG.

If the average QTcF from the three ECGs is > 500 ms or increased by > 60 ms above baseline, the following actions must be taken:

- Withhold study treatment
- Immediately notify the Sponsor
- Hospitalize symptomatic subjects (eg, with palpitations, dizziness, syncope, orthostatic hypotension, a significant ventricular arrhythmia on ECG) for a thorough cardiology evaluation and management
- Consider cardiology consultation for asymptomatic subjects for evaluation and management
- Check electrolytes, especially magnesium, potassium and calcium; correct abnormalities as clinically indicated
- Check concomitant medications for any medication that may have contributed to QT prolongation, and if possible, discontinue these medications (<http://www.qtdrugs.org>)
- Repeat ECG triplicates hourly until the average QTcF is  $\leq$  500 msec, or otherwise determined by consultation with a cardiologist or appropriate expert.

Subjects with QTc prolongation and symptoms must be monitored closely until the QTc elevation and symptoms have resolved. Study treatment may be restarted at a reduced dose level if all of the following conditions are met:

- Symptoms are determined to be unrelated to the QT interval prolongation
- The QTcF value > 500 ms or increase of > 60 ms above baseline is not confirmed according to protocol procedures
- Study treatment has been interrupted through a minimum of 1 week following the return of the QTcF to  $\leq$  500 msec or return to  $\leq$  60 ms above baseline.
  - QT prolongation can be unequivocally associated with an event other than cabozantinib administration and is treatable/has been resolved
  - Sponsor has reviewed all available information and has agreed to the continuation of study treatment

Following re-initiation of study treatment, ECGs must be repeated weekly for 2 weeks, then every 2 weeks for 1 month, then according to the protocol-defined time points.

All study treatment must be permanently discontinued if either of the following applies:

- Cardiac evaluation confirms that symptoms are the consequence of QT interval prolongation
- Recurrence of QTcF prolongation (confirmed by central ECG lab) after reinitiation of study treatment at a reduced dose

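### Section 7.2 withholds drug when QTcF prolongation is confirmed but allows restart only if it was not confirmed, so on the natural reading its restart provisions cannot operate

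*Combined protocol and SAP*

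**What the plan says.** The subsection on corrected QT prolongation in Section 7.2 works in stages.

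- **Confirmation.** After a first ECG over the limits, "two additional ECGs must be performed with intervals not less than 3 min apart within 30 min after the initial ECG".
- **Trigger and action.** "If the average QTcF from the three ECGs is > 500 ms or increased by > 60 ms above baseline", a list of actions follows, the first being "Withhold study treatment". This is the only withhold instruction in the subsection.
- **Restart.** "Study treatment may be restarted at a reduced dose level if all of the following conditions are met". Five conditions follow. The second is "The QTcF value > 500 ms or increase of > 60 ms above baseline is not confirmed according to protocol procedures". The third begins "Study treatment has been interrupted through a minimum of 1 week following the return of the QTcF to" and then names the same two limits. The fourth is "QT prolongation can be unequivocally associated with an event other than cabozantinib administration and is treatable/has been resolved". The first concerns whether symptoms are related to the QT finding, and the fifth is sponsor review and agreement.
- **After restart.** ECGs are repeated on a set schedule once treatment is re-initiated.
- **Permanent discontinuation.** Two situations are listed: symptoms shown to be caused by QT prolongation, and "Recurrence of QTcF prolongation (confirmed by central ECG lab) after reinitiation of study treatment at a reduced dose".

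**The concern.** The withhold trigger and the second restart condition use the same two limits with opposite outcomes. Treatment stops because the triplicate was over the limits, and may resume only if the prolongation was not confirmed. If the triplicate is what confirms it, recovery, cause and sponsor review cannot change the answer for a patient withheld under this subsection.

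Safety and tolerability is a primary aim (Section 3). Two investigators facing the same recovered patient could act in opposite ways, each citing this subsection. One would keep the patient off drug because the second condition fails. The other would restart because the return-to-limits, other-cause and sponsor-agreement conditions plainly contemplate it. With 11 patients planned (Section 6), a single such decision would show in time on drug and in the tolerability summary.

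**Working it through.** The point is one of logic, and the plan gives no figure to reproduce. The check sets the provisions side by side.

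**Step 1: the rule in symbols.** Let C mean that the triplicate average is above 500 ms or more than 60 ms over baseline. Let K mean that the prolongation is confirmed in the sense of the second restart condition. Let R stand for the other four conditions.

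- Withheld under this subsection: C
- Restart permitted: (not K) and R
- Withheld and later restarted: C and (not K) and R

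If K is the triplicate result, then K = C, and the third line contains C and (not C). It is empty for every ECG value, even with all of R true. Enumerating baselines and averages would add nothing, because the zero follows from the wording. The patients who do satisfy not K are those whose average fell within the limits. The subsection never withholds drug from them, so they have nothing to restart.

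**Step 2: what else K could mean.**

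| Reading of confirmed | Can a withheld patient restart? | Support in the text |
|---|---|---|
| The triplicate after the first ECG | No | Only confirmation step described for a first event; same limits |
| A central over-read of the triggering tracing | Yes, if the over-read is negative | Central laboratory named only for recurrence; no central reading in the Section 7 schedule |
| Later repeat ECGs, including the hourly triplicates | Yes, on recovery | Largely duplicates the separate return-to-limits condition |
| A separate route, not a joint condition | Yes | Contradicted by the lead-in, which requires all conditions |

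**Step 3: does the subsection intend a permanent stop?**

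| Provision in the same subsection | What it presupposes |
|---|---|
| One-week interruption after QTcF returns within limits | Prolongation was real and has resolved |
| Prolongation attributed to another cause | Prolongation was real |
| ECG schedule after re-initiation | Restart happens |
| Stop on recurrence after restart at a reduced dose | Restart happens |
| Two-item permanent-discontinuation list | A first confirmed prolongation is not by itself a permanent stop |

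Under the triplicate reading, a first confirmed prolongation becomes a third, unlisted permanent stop. The post-restart schedule and the recurrence rule then cannot be reached after a hold under this subsection.

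**Step 4: how likely, and how large.** No event rate is given. Section 7.1 (Warnings and Precautions) reports prolongation of 10 to 15 ms with QTcF not above 500 ms. Section 5 admits patients with QTc up to 480 ms. From that cap, 480 + 15 = 495 ms stays within the absolute limit, but a rise of more than 500 − 480 = 20 ms crosses it. One patient is 1/11 = 9.1 percentage points of the disease control rate, or 1/10 = 10 points at the sample of 10 used in Section 14.4. That shift occurs only if such an event happens and the decision changes that patient's disease-control status.

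**The case against.** The strongest reply is that the phrase about protocol procedures is undefined. The subsection mentions a central ECG laboratory and orders repeated triplicates after the hold, so confirmation might mean something later than the first triplicate. In the extracted text, the last two restart conditions are also indented beneath the third, which could be the remnant of a branched list. These points show that the contradiction rests on a reading. They do not remove it. The laboratory is tied only to recurrence, the repeat-ECG reading duplicates another condition, the indentation may come from PDF extraction, and the disputed condition stands at the top level under a lead-in requiring all of them.

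A reader might infer that no patient whose drug is interrupted could ever restart. The documents do not support that. The general adverse event table in Section 7.1 allows interruption with no triplicate, so a patient interrupted there for symptoms, with an average within limits, could meet the second condition. Such interruptions are outside this point.

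A reader might also infer a material threat to the primary efficacy result. That is not shown either. The reported QT changes are small, and QT-prolonging drugs are excluded at entry (Section 5), although Section 7.2 does not explicitly bar them later. Enrolment is through one programme (Section 6), and sponsor agreement is itself a restart condition, which limits inconsistent handling. With 11 patients the rule may never be invoked.

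**Conclusion.** The conflict stands for holds made under the QTc subsection. On the natural reading, a patient withheld there cannot satisfy the restart list, while five other provisions of the same subsection presuppose that restart is possible. A safety rule that fails when followed as written should be corrected even if it is seldom used.

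The conclusion rests on two assumptions: that confirmation means the first-event triplicate, and that the listed conditions apply jointly, as the lead-in says. It alters no estimand, analysis method or sample size. Any effect on the disease control rate is conditional on an event occurring and is not an expected bias.

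**What to change.** Amend the subsection on corrected QT prolongation in Section 7.2 as follows.

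1. Reconcile the withhold trigger with the restart list so that both can apply to the same patient, or say openly that a first confirmed prolongation ends treatment.
2. Define what counts as confirmed: which ECGs, read by whom, and when.
3. State whether the not-confirmed item is a joint condition or a separate route.
4. Align the post-restart ECG schedule, the recurrence rule with its central-laboratory wording, and the permanent-discontinuation list with that choice.

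Which clinical rule should govern is for the sponsor to decide. The cost is a wording amendment to one list and its linked rules. Clarifying the text does not in itself add visits, assessments or patients.

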## 8. Safety

### 8.1 Adverse Events

An AE is any untoward medical occurrence in a patient or clinical investigation subject who has been enrolled in a clinical study and who may have been given an investigational product, regardless of whether or not the event is assessed as related to the study treatment. An AE can therefore be any unfavorable and unintended sign (including an abnormal laboratory finding), symptom, or disease temporally associated with the use of an investigational product, regardless of whether or not the event is assessed as related to the investigational product. Pre-existing medical conditions that worsen during a study should be recorded as AEs. Abnormal laboratory values, ECG findings, or vital signs are to be recorded as AEs if they meet the criteria described in Section 7.0. All Adverse Events will be graded using CTCAE v5.0. per section 9.1 of this protocol.

All untoward events that occur after informed consent through 30 after the decision to discontinue study treatment (or the date the subject is deemed to be a screen failure) are to be recorded by the investigational site. This requirement includes AEs from unscheduled as well as scheduled visits.

Assessment of the relationship of the AE to the study treatment by the investigator is based on the following two definitions:

- Not Related: A not-related AE is defined as an AE that is not associated with the study treatment and is attributable to another cause or there is no evidence to support a causal relationship;
- Related: A related AE is defined as an AE where a causal relationship between the event and the study treatment is a reasonable possibility. A reasonable causal relationship is meant to convey that there are facts (eg, evidence such as dechallenge/rechallenge) or other clinical arguments to suggest a causal relationship between the AE and study treatment.

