## 7.1 Dose Modifications

### Dose Modifications of Cabozantinib for Treatment-Related AEs

CTCAE v.5.0 Grade	Recommended Guidelines for Management a
Grade 1 AEs	Add supportive care as indicated. Continue cabozantinib treatment at the current dose level if AE is manageable and tolerable.
Grade 2 AEs which are tolerable and are easily managed	Continue cabozantinib treatment at the current dose level with supportive care.
Grade 2 AEs which are intolerable and cannot be adequately managed	At the discretion of the investigator, cabozantinib should be dose reduced or interrupted.  Note: It is recommended that dose holds be as brief as possible.
Grade 3 AEs (except clinically non-relevant laboratory abnormalities)	Cabozantinib should be interrupted unless the toxicity can be easily managed with a dose reduction and optimal medical care.  Note: It is recommended that dose holds be as brief as possible.
Grade 4 AEs (except clinically non-relevant laboratory abnormalities)	Subjects should have cabozantinib interrupted immediately. Discontinue cabozantinib unless the following criteria are met: 
 
• Subject is deriving clear clinical benefit as determined by the investigator and agreed by the Sponsor
 
• Toxicity can be managed with a dose reduction following recovery to Grade 1 (or baseline) and optimal medical care
 

AE, adverse event.

Note: The dose delay and modification criteria for specific medical conditions are provided below.

a Study treatment dose adjustment is only needed if the toxicity was deemed related to cabozantinib treatment or had an unclear relationship to cabozantinib treatment.

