## Warnings and Precautions and Guidelines for the Management of Adverse Events

The most frequent adverse events experienced by  $\geq 20\%$  of subjects treated with cabozantinib were diarrhea, fatigue, nausea, decreased appetite, vomiting, weight decreased, PPES, constipation, hypertension, dysgeusia, dysphonia, and asthenia.

Adverse events associated with laboratory abnormalities experienced by  $\geq 5\%$  of subjects treated with cabozantinib include anemia, AST increased, ALT increased, hypothyroidism, hypokalemia, hypomagnesemia, thrombocytopenia, hypocalcemia, hypophosphatemia, lipase increased, lactate dehydrogenase (LDH) increased, neutropenia, ALP increased, hyponatremia, and leukopenia. Mild to moderate QTc interval prolongation (10-15ms) has also been observed with a QT interval calculated by the Fridericia formula (QTcF) not exceeding 500 ms.

Subjects may also experience medically important but less frequent adverse events including arterial and venous thrombotic AEs (eg, DVT, pulmonary embolism [PE], transient ischemic attack [TIA], and myocardial infarction [MI]), severe hemorrhagic events, proteinuria, wound healing complications, GI perforation, abscesses including intra-abdominal and pelvic abscess, GI and non-GI fistulae formation, osteonecrosis, and reverse posterior leukoencephalopathy syndrome (RPLS).

Cabozantinib treatment should be permanently discontinued for the following adverse events: visceral perforation or fistula formation, severe hemorrhage, serious arterial thromboembolic events, nephrotic syndrome, malignant hypertension, hypertensive emergency, persistent uncontrolled hypertension despite optimal medical management, osteonecrosis of the jaw (ONJ), and RPLS.

Guidelines for the management of AEs (ie, dose interruptions and dose reductions) are presented in the next sections. Each dose reduction of cabozantinib should be to one dose level lower than the current dose. Dose reductions of more than one dose level are acceptable per Investigator judgment. All AEs should also be managed with supportive care at the earliest signs of toxicity. Adverse reactions are presumed to be attributable to study drug. Adverse events classified as “not related” are defined as AEs that are, without question, not associated with the study treatment and definitely attributable to another cause.

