### 14.3.2 Safety Population

The safety population comprises all patients who have received at least one dose of the study medication. This set will be used for safety analysis.

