## 14.5 Safety Analysis

The safety set will be used for all safety analysis. All safety data will be listed. For the treatment-emergent AEs, namely AEs started or worsened during the on-treatment period, the incidence will be summarized by system organ class and/or preferred term, severity based on CTCAE 5.0 grades, type of adverse event and the relation to the

study drug. Deaths reportable as SAEs and non-fatal serious adverse events will be listed by patient and tabulated by type of adverse event.

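### Do the two wordings of a 'not related' adverse event in Sections 7.1 and 8.1 leave the safety tables without a usable causality rule?

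*Combined protocol and SAP*

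**What the plan says.** Section 8.1 introduces its causality rule with "Assessment of the relationship of the AE to the study treatment by the investigator is based on the following two definitions". An event is not related if it "is not associated with the study treatment and is attributable to another cause or there is no evidence to support a causal relationship". It is related if causation is a reasonable possibility, which the section explains as meaning that "there are facts (eg, evidence such as dechallenge/rechallenge) or other clinical arguments to suggest a causal relationship between the AE and study treatment". There are only these two categories.

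Section 7.1, under the heading on warnings, precautions and management of adverse events, starts from a presumption that reactions are due to the drug. It adds that events classed as not related "are defined as AEs that are, without question, not associated with the study treatment and definitely attributable to another cause". The paragraph containing that sentence opens with "Guidelines for the management of AEs (ie, dose interruptions and dose reductions) are presented in the next sections". Footnote a to the dose-modification table in the same section says that dose adjustment is "only needed if the toxicity was deemed related to cabozantinib treatment or had an unclear relationship" to the drug.

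Section 14.5 summarises the incidence of treatment-emergent events by several factors, including "type of adverse event and the relation to the" study drug. The denominator is set in Section 14.3.2: "The safety population comprises all patients who have received at least one dose of the study medication". The label also decides which late serious events are listed for the SAE form (Section 8.3), which unexpected serious events go to regulators (Section 8.4) and which events are followed beyond 30 days (Section 9.4).

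**The concern.** Section 7.1 allows the not-related label only when another cause is certain. Section 8.1 also allows it when there is simply no evidence for the drug. An event of undetermined cause could therefore be labelled either way by an investigator acting in good faith. The Section 7.1 sentence is worded as a definition, neither section refers to the other on causality, and no sentence says which prevails. Footnote a adds an uncertain state that Section 8.1 does not name.

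The setting makes this worth checking. The trial has one arm, so there is no control group to separate drug effects from disease effects, and attribution carries more weight than it would in a randomised trial. Attribution can also change a reported incidence a good deal: in the pooled data of Table 2-1, constipation falls from 32.3% (all) to 14.3% (related) and dyspnoea from 20.6% to 7.8%. If labels were assigned under mixed rules, the by-relation table would be hard to interpret and the rule behind each label hard to recover later.

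**Working it through.** The plan states no figure on this point, so the first step is to apply each definition to the possible combinations.

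| Fact or argument for the drug | Definite other cause | Section 7.1 | Section 8.1 |
|---|---|---|---|
| Yes | No | Related | Related |
| No | Yes | Not related | Not related |
| No | No | Cannot be not related | Not related |
| Yes | Yes | Premise contradicts itself | Premise contradicts itself |

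The definitions separate only in the third row. The placing of the 'or' in Section 8.1 does not remove the difference. Whether absence of evidence stands alone or is joined to the words before it, a definite other cause is not required.

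The second step is to ask which definition each use of the label draws on.

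- Section 8.1 says that its two definitions are the basis of the investigator's assessment, and the closing paragraph of Section 8.3 gives that assessment to the investigator.
- Sections 8.3, 8.4, 9.4 and 14.5 all use that label.
- Section 8.1 refers back to Section 7 when it wants Section 7 to apply, namely for deciding which laboratory, ECG and vital-sign findings count as adverse events. It makes no such reference for causality.
- The Section 7.1 sentence and footnote a both sit in guidance on interrupting and reducing the dose. The uncertain state in footnote a is part of that guidance and does not need a matching category in a two-way reporting label.

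The third step is the size of a change of label. The inputs are 11 planned patients (Section 6) and the 10 used in the table of Section 14.4. For a patient whose only related event of a given type changes label, the shift is 1/n:

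- n = 11: 1/11 = 9.1 percentage points
- n = 10: 1/10 = 10.0 percentage points
- n = 8, the lower end of an assumed range of 8 to 11 treated patients: 1/8 = 12.5 percentage points

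The shift is 0 if the patient has another related event of the same type. The documents do not show how many events would fall in the third row, so no total effect can be calculated.

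**The case for a change.** The best case for a change is that scope is inferred and not written. The Section 7.1 sentence is not limited to dosing by its own words, the outputs affected serve a primary aim, and one sentence would settle the matter. The manufacturer's right in Section 8.4 to upgrade an assessment covers serious events only. It does not reach non-serious events in the by-relation table, or non-serious events that led to discontinuation and qualify for follow-up under Section 9.4.

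The difference in wording stands, and so does the absence of an express order of precedence. The consequences are weaker than they first appear.

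- **Late serious events.** Section 8.3 requires the 24-hour notice to the manufacturer on an SAE form even when the event is thought unrelated, and that instruction carries no time limit of its own. Section 11 (OnCore safety reporting) captures every serious event, with attribution to drug, procedure, disease or other cause. The list in Section 8.3 does turn on relatedness after 30 days, so the risk of a missed record is reduced but not removed.
- **Regulatory reports.** Section 8.4 ties these to an outside regulation. Whether any report would differ depends on the causality standard there, which the documents do not give.
- **Remedy.** A new sentence could place undetermined events in either category and be workable. It would record a choice that Section 8.1 already makes, with no result shown to improve.

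**Conclusion.** The concern identifies a real difference in wording, but it does not call for a change to the plan. An analyst or investigator following Section 8.1 as written has a complete two-way rule, including for events of undetermined cause, and can build the by-relation table from it. Enrolment through a single programme (Section 6) also limits the scope for different readings.

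The possible effect is confined to the related column of a descriptive table and the reporting steps tied to it: 9.1 to 12.5 percentage points per affected patient and event type if 11 down to 8 patients are treated, and 0 where another related event of that type remains. All-cause incidence, the full listings, the 24-hour notice, OnCore capture and the trigger for notifying the data and safety monitoring committee do not depend on the label. Section 14.5 plans no test or interval for adverse-event incidence, and Section 14.7 plans no interim analysis.

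This conclusion assumes that investigators label events by Section 8.1, as that section says. It takes no position on the dose-adjustment guidance in Section 7.1.
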